3.6.3 Additional safety assessments

3.6.3.1 Laboratory variables, vital signs and electrocardiograms (ECGs)

The following laboratory variables, vital signs and electrocardiogram (ECG) variables will be analyzed. They will be converted into standard international units.

- Hematology:
 - Red blood cells and platelets and coagulation: hemoglobin, hematocrit, mean corpuscular volume, mean corpuscular hemoglobin, red blood cell count, %Reticulocytes, platelet count
 - White blood cells: white blood cell count, neutrophils, lymphocytes, monocytes, basophils, eosinophils
- Clinical chemistry:
 - Metabolism: glucose, [REDACTED] total protein, albumin, creatine phosphokinase
 - Electrolytes: sodium, potassium, chloride, calcium, calcium corrected, bicarbonate
$$\text{Calcium Corrected (mmol/L)} = \text{Total calcium (mmol/L)} + 0.8 * 0.25 * [4 - \text{Serum albumin (g/L)} * 0.1]$$
 - Renal function: creatinine, creatinine clearance, blood urea nitrogen.
Creatinine clearance will be derived with the equation of Cockcroft and Gault using weight assessed at the same visit as creatinine.
 - Liver function: alanine aminotransferase (ALT), aspartate aminotransferase (AST), alkaline phosphatase, total and direct bilirubin
 - Pregnancy test: Serum β -human chorionic gonadotropin (choriogonadotropin Beta as needed for women of childbearing potential)
- Vital signs: sitting heart rate, sitting systolic and diastolic blood pressure, temperature.
- ECG variables: heart rate, PR, QRS, QT, and corrected QTcF. The average of the triplicate ECG assessments will be used.

Data below the lower limit of quantitation/detection limit (LLOQ) will be replaced by half of the LLOQ, data above the upper limit of quantification will be replaced by ULOQ value.

Quantitative analyses

When relevant, for laboratory variables, vital signs and ECG variables above, descriptive statistics for results and changes from baseline will be provided for each planned visit, the last value and the worst value (minimum and/or maximum value depending on the parameter) during the on-treatment period. These analyses will be performed using central measurements only for laboratory variables and ECG variables.

For selected laboratory variables including hemoglobin, hematocrit, erythrocyte, platelets, leukocytes, neutrophils, lymphocytes, monocytes, glucose, cholesterol, triglycerides, sitting systolic blood pressure, sitting diastolic blood pressure, and sitting heart rate mean changes from baseline with the corresponding standard error will be plotted over time.

Analyses according to PCSA

Potentially clinically significant abnormality (PCSA) analyses will be performed based on the PCSA list currently in effect at Sanofi at the time of the database lock. For parameters for which no PCSA criteria are defined, similar analyses will be done using the normal range, if applicable.

Analyses according to PCSA will be performed based on the worst value during the treatment-emergent period, using all measurements (either local or central, either scheduled, nonscheduled or repeated).

For laboratory variables, vital signs and ECG variables above, the incidence of participants with at least one PCSA during the treatment-emergent period will be summarized regardless of the baseline level and according to the following baseline status categories:

- Normal/missing
- Abnormal according to PCSA criterion or criteria

In case of missing local assay methods, they will be considered similar as those used in central lab for the analysis of PCSA as soon as the laboratory parameters correspond to the PCSA reference table.

Even if the local and central specimen are different, they can be considered similar for the analysis of PCSA as soon as the laboratory parameters correspond to the PCSA reference table.

Additional analyses for drug-induced liver injury

The following additional analyses will be performed for drug-induced liver injury:

- Time to onset of the initial alanine aminotransferase (ALT) or aspartate aminotransferase (AST) elevation ($>3 \times \text{ULN}$) and total bilirubin elevation ($>2 \times \text{ULN}$) during the treatment-emergent period may be analyzed using Kaplan-Meier method.
- A graph of the distribution of peak values of ALT versus peak values of total bilirubin during the treatment-emergent period will be provided.
- For each liver function test (eg, ALT), participants having experienced a PCSA (eg, ALT $>5 \text{ ULN}$) will be summarized using the following categories: Returned to baseline PCSA status (or returned to value $\leq \text{ULN}$ in case of missing baseline) before last IMP dose, returned to baseline PCSA status after last IMP dose, Never returned to baseline PCSA status, No assessment after elevation. This summary will be performed by categories of elevation (ALT $>3, >5, >10, >20 \text{ ULN}$).

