**Table 7 - Protocol-required laboratory tests**

Laboratory tests	Parameters
Hematology	Platelet count Red blood cell (RBC) count RBC indices: Mean corpuscular volume (MCV) Mean corpuscular hemoglobin (MCH) %Reticulocytes White blood cell (WBC) count with differential: Neutrophils Lymphocytes Monocytes Eosinophils Basophils Hemoglobin Hematocrit
Clinical chemistry a	Bicarbonate Blood urea nitrogen (BUN) Potassium Creatinine Creatinine clearance Glucose non-fasting Sodium Calcium Chloride Phosphate AST/Serum glutamic-oxaloacetic transaminase ALT/Serum glutamic-pyruvic transaminase ALP b Albumin Total bilirubin

Laboratory tests	Parameters
	Conjugated bilirubin
	Unconjugated bilirubin
	Total protein
	CPK
	Total cholesterol fasting
	
Pregnancy testing	[Serum or highly sensitive urine] human chorionic gonadotropin (hCG) pregnancy test (as needed for women of childbearing potential) c
Other screening tests	FSH (as needed in women of nonchildbearing potential only)  Serology (QuantiFERON®, HIV (HIV-1 and HIV-2) antibodies/CD4 count, HBsAg, IgM and total HBcAb and HCVAb. In case of HBcAb positivity, HBV-DNA testing must be performed. In case of HCVAb positivity, HCV-RNA testing must be performed (for Japan, HBsAb needs to be tested in addition to HBsAg and (IgM or total) HBcAb - Section 10.7.3 )  hsCRP  All study-required laboratory tests will be performed by a central laboratory except for urine pregnancy.

NOTES:

- a Details of liver chemistry stopping criteria and required actions and follow-up are given in [Section 7.1.2 Liver Chemistry Stopping Criteria and Appendix 6 \(Section 10.6\)](#).
- b If alkaline phosphatase is elevated, consider fractionating.
- c Local urine testing will be standard for the protocol unless serum testing is required by local regulation or IRB/IEC.

Investigators must document their review of each laboratory safety report.

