### Evaluate Increase in ALT\*\*\*

[figure not shown]
- 1. INFORM** the Site Monitor who will forward the information to the Study Manager
- 2. INVESTIGATE** specifically for malaise with or without loss of consciousness, dizziness, and/or hypotension and/or episode of arrhythmia in the previous 72 hours; rule out muscular injury
- 3. INVESTIGATE** if any recent alcohol use or travel
- 4. INVESTIGATE** if any use of non-prescription medications including herbal or dietary supplements
- 5. PERFORM** the following tests:
  - LFTs: AST, ALT, alkaline phosphatase, GGT, total and conjugated bilirubin and prothrombin time / INR
  - CPK, serum creatinine, complete blood count
  - Anti-HAV IgM, anti-HBc IgM, (HBV-DNA if clinically indicated), anti-HCV and HCV RNA, anti-CMV IgM and anti-HEV IgM antibodies
  - Depending on the clinical context, check for recent infection with EBV, herpes viruses, and toxoplasma
  - Hepatobiliary ultrasonography (or other imaging investigations if needed)
- 4. CONSIDER** Auto-antibodies: antinuclear, anti-DNA, anti-smooth muscle, anti-LKM
- 5. CONSIDER** iron, ferritin and transferrin
- 6. CONSIDER** biomarkers for alcohol use (eg, urine ethyl glucuronide (EtG)]
- 7. CONSIDER** consulting with hepatologist
- 8. CONSIDER** patient hospitalization if INR>2 (or PT<50%) and/or central nervous system disturbances suggesting hepatic encephalopathy
- 9. MONITOR LFTs after discontinuation of IMP:**
  - As *closely as possible* (or **every 48 hours**) until stabilization, then every 2 weeks until return to  $\leq$ ULN, baseline value (if baseline  $>$ ULN) or clinical resolution.
- 10. FREEZE** serum sample (5ml x 2)
- 11. In case of suspicion of GILBERT Syndrome**, a DNA diagnostic test should be done

**INCREASE IN SERUM CREATININE in patients with normal baseline  
(creatininemia between 45 µmol/L and 84 µmol/L)**

Increase in serum creatinine is to be recorded as an AE only if at least 1 of the criteria listed in the general guidelines for reporting adverse events in [Section 8.4](#) is met.

**INCREASE IN CPK OF NON-CARDIAC ORIGIN AND NOT  
RELATED TO INTENSIVE PHYSICAL ACTIVITY**

Increase in CPK is to be recorded as an AE only if at least 1 of the criteria in the general guidelines for reporting adverse events in [Section 8.4](#) is met.

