3 STATISTICAL ANALYSES

3.1 GENERAL CONSIDERATIONS

In general, continuous data will be summarized using the number of observations available, mean, standard deviation (SD), median, Q1, Q3, minimum, and maximum. Categorical and ordinal data will be summarized using the count and percentage of participants. The graphical plots will be presented for selected endpoints including primary, secondary and some exploratory endpoints.

The baseline value is defined as the last available value before the first dose of double-blind investigational medicinal product (IMP). For participants randomized but not treated, the baseline value is defined as the last available value before randomization.

Unless otherwise specified, analyses will be performed by intervention group/dose level (and overall for baseline and demographics characteristics).

Observation period

The observation period will be divided into 4 segments:

- The **pre-treatment period** is defined as the period up to first double-blind investigational IMP administration.
- The **treatment-emergent (TE) period** is defined as the period from the first IMP administration to the last IMP administration + 5 days. The treatment-emergent period includes the following 2 periods:
 - The **on-treatment period** is defined as the period from the first IMP administration to the last administration of the IMP + 1 day.
 - The **residual treatment period** is defined as the period from the end of the on-treatment period to the end of the treatment-emergent period.
- The **post-treatment period** is defined as the period from the end of the treatment-emergent period.

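### The ALT-versus-bilirubin graph stops at last dose + 5 days, so a bilirubin rise first seen later in the protocol's own liver follow-up is not paired with the earlier ALT peak in any planned liver-injury analysis

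*SAP*

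**What the plan says.** SAP 3.1 defines the treatment-emergent period: it "is defined as the period from the first IMP administration to the last IMP administration + 5 days". Protocol 9.2.1 has the same definition.

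SAP 3.6.3.1 applies that period to three liver-related outputs:

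- The peak graph: "A graph of the distribution of peak values of ALT versus peak values of total bilirubin during the treatment-emergent period will be provided".
- Time to onset of ALT or AST above 3 x ULN and total bilirubin above 2 x ULN, which "during the treatment-emergent period may be analyzed using Kaplan-Meier method".
- Incidence of potentially clinically significant abnormalities: "Analyses according to PCSA will be performed based on the worst value during the treatment-emergent period".

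A fourth output, the recovery table, does look past the last dose. For each liver test it records whether an abnormal value returned to its baseline status.

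On the clinical side, note a to Protocol Table 7 reads "Details of liver chemistry stopping criteria and required actions and follow-up are given in" Section 7.1.2 and Appendix 6. The ALT box in Appendix 6 lists the work-up as "LFTs: AST, ALT, alkaline phosphatase, GGT, total and conjugated bilirubin and prothrombin time / INR". It then instructs sites: "MONITOR LFTs after discontinuation of IMP". Testing is to be as close as possible, or every 48 hours, "until stabilization, then every 2 weeks until return to" the upper limit of normal or baseline, or clinical resolution. The Schedule of Activities also has laboratory tests at Visit 7, 4 weeks after the last dose.

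**The concern.** The graph exists to find participants in whom a transaminase rise is joined by a bilirubin rise. The two peaks need not fall on the same day. If IMP is permanently stopped because of the liver finding, the stop itself sets the end of the analysis window 5 days later, while the protocol goes on collecting the paired liver tests.

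Take a participant with ALT above 3 x ULN on drug whose bilirubin first exceeds 2 x ULN on day 8 after stopping. The graph would place this person at the highest bilirubin seen up to day 5, which is not above 2 x ULN. Protocol 10.3.2 names the combination of ALT above 3 x ULN and total bilirubin above 2 x ULN among its medically important events. Protocol 2.3.1 reports four ALT-elevation AESIs in the multiple-dose study. In a graph of this kind a single participant in the wrong region changes the reading.

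**Working it through.** The plan gives no figure to reproduce here. The check compares the analysis window with the dates on which liver tests are due.

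**Inputs**

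- Window after last dose: 5 days (SAP 3.1; Protocol 9.2.1).
- Tests after a liver-related stop: every 48 hours until stable, then every 2 weeks (Protocol Appendix 6).
- EoT visit after early discontinuation: up to day 7 after the last dose (Protocol 7.1.1; Schedule of Activities, footnote a).
- Week 12 visit on Day 85; final visit on Day 113 ± 3 (Schedule of Activities).
- Terminal half-life: about 20 to 30 hours (Protocol 4.3).

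**Step 1: 48-hour tests.** Count tests from the last dose, at days 2, 4, 6 and so on. A test counts if its day is 5 or less, so only days 2 and 4 do. The 48-hour phase lasts only until values stabilise, so the horizons below are illustrations.

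| 48-hour testing up to | Tests due | Inside window | Outside |
|---|---|---|---|
| Day 14 | 14/2 = 7 | 2 | 5 |
| Day 28 | 28/2 = 14 | 2 | 12 |

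**Step 2: two-weekly tests.** If values stabilise on or after the day of the last dose, the first two-weekly test is at day 14 or later. Since 14 > 5, none of these tests count.

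**Step 3: scheduled visits.**

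- EoT after early discontinuation: a draw on day 6 or 7 is permitted and falls outside.
- Final visit for a completer: the window ends on Day 85 + 5 = Day 90. The visit falls on Days 110 to 116, which is 25 to 31 days after a Day 85 last dose, and is always outside.
- Of the 28 days of follow-up after the last dose, 28 − 5 = 23 are outside: 23/28 = 82%.
- SAP 1.1 keeps a 2-week follow-up for participants enrolled under earlier protocol versions. That visit is also beyond day 5.

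**Step 4: does another planned output make the pairing?**

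| Output | Uses values after day 5? | Pairs ALT with bilirubin? |
|---|---|---|
| Peak graph | No | Yes |
| Time to onset (optional) | No | Yes |
| PCSA incidence | No | No |
| Recovery table | Yes, for recovery | No, one test at a time |
| By-visit summaries | Possibly, at the final visit | No |
| Post-treatment SAE table (SAP Table 6) | Yes | Only if the case is reported and coded as an SAE |

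No row has both a later window and a laboratory-based pairing.

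**Step 5: what the 5 days represent.** Five days is 120 hours. 120/30 = 4 half-lives leaves 2^-4 = 6.25% of drug; 120/20 = 6 half-lives leaves 2^-6 = 1.6%. The window matches washout of the drug. It does not match the length of the liver follow-up.

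**The case against.** **The window has a rationale.** It covers 4 to 6 half-lives, is prespecified in the protocol, and is used consistently for TEAEs and PCSA. This stands as a reason to keep the treatment-emergent graph. It does not justify omitting the later course of an injury that began on drug and that the protocol follows to resolution.

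**It is tempting to say that any ALT rise stops IMP and so closes the window.** The documents do not support that. The stopping level is not visible in the public text. Protocol 7.1.1 has abnormal values rechecked before permanent discontinuation, 7.1.4 and 7.1.5 allow interruption and rechallenge, and Appendix 6 mentions a 72-hour retest. The window runs to the last administration, so an interruption followed by a restart lies inside it. The point holds only for permanent stops and for rises after the end of treatment.

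**It is tempting to put a percentage on the missed cases.** That needs a distribution for the lag between the stop and the bilirubin rise, and the documents give none. What matters is also when bilirubin first exceeds 2 x ULN, not when it peaks. A participant who crosses by day 5 is already in the right region.

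**A reader might infer that the case vanishes from safety reporting.** It does not. The combination is on the protocol's list of medically important events, post-treatment SAEs are tabulated by SOC and PT, and the IDMC reviews unblinded safety and laboratory data. In about 207 participants such a case would probably be noticed. Nor can an ALT-related AESI analysis in hidden text be ruled out. These routes limit the harm, but the visible ones depend on reporting and coding rather than on the laboratory data.

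**Extending the window creates unequal ascertainment.** Participants with ALT rises are tested until resolution. Those who stop IMP but stay in the study have no routine laboratory tests after EoT. This stands, and it weighs most on the Kaplan-Meier analysis, which should therefore not be extended. That analysis is in any case optional and uses first threshold crossing, not peaks.

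**Conclusion.** The gap is real but narrow. For a participant who permanently stops IMP, or who completes treatment, a total bilirubin above 2 x ULN first seen more than 5 days after the last dose is not paired with an earlier ALT peak in any liver-injury analysis that the SAP describes. Under 48-hour testing counted from the last dose, two draws fall inside the window; later ones, the two-weekly draws and the Week 16 draw fall outside.

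The conclusion rests on the visible text and assumes that no hidden analysis makes the pairing. It does not say that such a participant would be plotted with normal bilirubin, only that the plotted value is the peak up to day 5. The number affected is unknown and may be zero. This is a cheap improvement to the safety outputs. It is not a flaw in the trial's safety monitoring.

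**What to change.** In SAP 3.6.3.1:

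1. Keep the treatment-emergent ALT-versus-bilirubin graph as planned.
2. Add a second panel using all post-baseline ALT (and AST) and total bilirubin values, local or central, through the last follow-up value. Mark each point whose ALT, AST or bilirubin peak falls after the treatment-emergent period.
3. Add a listing of participants with ALT or AST above 3 x ULN and total bilirubin above 2 x ULN at any post-baseline time, with dates relative to the last dose.
4. Leave the optional Kaplan-Meier time-to-onset analysis on the treatment-emergent period.

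The cost is a few lines of SAP text, a changed date filter and one listing. No samples are needed beyond those the protocol already calls for, and no clinical procedure changes. The downside is small: late rises from other causes may appear, and participants with ALT rises are observed for longer than others. The marking and the retained treatment-emergent panel make both visible.

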3.7 OTHER ANALYSES

3.7.1 Other variables and/or parameters

3.7.1.1 PK analyses

All PK analyses will be conducted on the PK population. The data after receiving the wrong dose will be excluded from PK analyses. The exception is that, if one participant receives the same wrong dose during the entire study treatment period, then this participant will be included in the PK analyses and the analyses will be done according to the dose received.

Individual plasma concentrations of SAR441566 will be listed by nominal visit and intervention group. Plasma concentrations of SAR441566 will be summarized using arithmetic and geometric means, standard deviation (SD), standard error of the mean (SEM), coefficient of variation (CV%), minimum, median and maximum by intervention groups. All concentration values below the lower limit of quantitation (LLOQ) will be treated as zero in all summary statistics. Graphical presentation of PK concentration over time may be provided if appropriate.

The PK parameters will be estimated by a population PK approach and will be presented in a separate report.

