1.2 OBJECTIVES AND ENDPOINTS

Table 1 - Objectives and endpoints

	Objectives	Endpoints
Primary	
 To demonstrate the superiority of SAR441566 over placebo in participants with moderate to severe plaque psoriasis, in the NTIP. 	
 Proportion of participants with a 75% or greater PASI score (Psoriasis Area and Severity Index score) improvement (reduction) from baseline (PASI75) at Week 12.
Secondary	
 To evaluate the efficacy of SAR441566 in plaque psoriasis as compared to placebo in the NTIP. 	
 PASI percent change from baseline to Week 12. Proportion of participants with static Psoriasis Global Assessment (sPGA) score 0 (complete clearance) or 1 (minimal disease) at Week 12.

Objectives	Endpoints

• To evaluate the safety of SAR441566.• To assess pharmacokinetics of SAR441566 in participants with moderate to severe plaque psoriasis.	
• Incidence of TEAE, SAEs, and AEs of AESIs.• Incidence of study IMP permanent discontinuations and study withdrawals due to TEAEs.• Participants with medically significant changes in vital signs, ECG, and/or laboratory evaluations.• Plasma pre-dose and post-dose concentrations of SAR441566.
Tertiary/Exploratory	

• To evaluate the efficacy of SAR441566 in plaque psoriasis as compared to placebo change over time.	
• PASI percent change from baseline to Week 4 and 8.   
• The proportion of participants with a 90% or greater PASI reduction from baseline (PASI90) at Week 4, 8 and 12.   
• The proportion of participants with PASI75 at Week 4, and 8.     

• To characterize the pharmacodynamic profile of SAR441566 in participants with plaque psoriasis.	
• Change in peripheral blood soluble biomarkers (including but not limited to hsCRP, IL-17A, IL-17F, 

Objectives	Endpoints

• To evaluate the impact of SAR441566 on health	
• Change in Dermatology Life Quality Index (DLQI)

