2 ANALYSIS POPULATIONS

The following populations for analyses are defined.

Table 3 - Populations for analyses

Population	Description
Screened	All participants who signed the ICF.
Randomized	All participants from screened population who have been allocated to a randomized intervention by IWRS regardless of whether the intervention was received.
Intent-to-treat (ITT)*	All randomized participants. Participants will be analyzed according to the intervention allocated by randomization.
Safety	All randomized participants who have taken at least 1 dose of study intervention, regardless of the amount of treatment administered. Participants will be analyzed according to the intervention they received, ie, "as treated" group.
Pharmacokinetic (PK)	All participants from the safety population with at least one post-baseline PK result with adequate documentation of dosing and sampling dates and times. Participants having received only placebo will not be part of the PK population. Participants will be analyzed according to the intervention they received.
Pharmacodynamic biomarker (PDy) population	All randomized participants who (a) had at least one dose of study intervention (SAR441566 or placebo) and (b) had a sample drawn for biomarker measurement and successfully analyzed at baseline and at one or more post-baseline visits. The assignment of patients to interventions will be "as treated".
NTIP	All randomized participants who have never received targeted immunotherapy for psoriasis. Participants will be analyzed according to the intervention allocated by randomization.
ETIP	All randomized participants who previously received targeted immunotherapy for psoriasis. Participants will be analyzed according to the intervention allocated by randomization.

* Randomized population and ITT population are the same population in this study.

Participants exposed to study intervention before or without being randomized will not be considered randomized and will not be included in any analysis population. The safety experience of these participants will be reported separately.

Randomized participants for whom it is unclear whether they took the study intervention will be considered as exposed and will be included in the safety population as randomized.

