3.7.1.3 Biomarker analyses

The biomarker analyses will be performed using PDy population defined in [Section 2](#).

The following biomarkers will be evaluated if applicable:

- Peripheral blood soluble biomarkers (including but not limited to hsCRP, IL-17A, IL-17F, IL-22, IL-19) from baseline to Week 4 and 12

• [REDACTED]
[REDACTED]

The following analyses will be performed if applicable:

- Descriptive statistics by treatment arm at baseline, intermediate timepoints and end of treatment
- Plots of fold changes from baseline in soluble protein biomarkers per treatment arm and visit
- Appropriate statistical methods based on the sample size such as linear mixed models, ANOVA (parametric), Kruskal-Wallis test, Wilcoxon signed rank test (non-parametric)
- Correlation of (a) biomarker results at baseline and (b) changes of biomarker results from baseline to post treatment visits with participant's clinical parameters

If measurement values below LLoQ occur, then the number of these values will be reported, computations and plots will be conducted setting values below LLoQ to LLoQ/2 and corresponding points in plots will be marked by dedicated symbols.

Additional analysis for the biomarkers listed above and other exploratory biomarkers (eg, gene expression and proteomics data and DNA genotype data) may be performed and will be summarized in a separate document.

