Study days are calculated considering Day 1 as the day of first administration of intervention (or the day of randomization for participant not exposed).

Table 11 - Time-window definition for PK endpoints analyses

Scheduled visit	Analysis visit	Targeted study day	Time-window (days)	
			PK Assessments	
Week 0 (Visit 2)	Week 0	1	2.5-3.5 hour after Day 1 dose	
Week 2 Pre-dose (Visit 3)	Week 2	15	1 hour before Day 7-21 dose	
Week 2 Post-dose (Visit 3)	Week 2	15	2.5-3.5 hour after Day 7-21 dose	
Week 4 Pre-dose (Visit 4)	Week 4	29	1 hour before Day 22-42 dose	
Week 4 Post-dose (Visit 4)	Week 4	29	2.5-3.5 hour after Day 22-42 dose	
Week 8 Pre-dose (Visit 5)	Week 8	57	1 hour before Day 43-70 dose	
Week 8 Post-dose (Visit 5)	Week 8	57	2.5-3.5 hour after Day 43-70 dose	
Week 12 Pre-dose (Visit 6)	Week 12	85	1 hour before Day >70 dose	
Week 12 Post-dose (Visit 6)	Week 12	85	2.5-3.5 hour after Day >70 dose	

Study days are calculated considering Day 1 as the day of first administration of intervention (or the day of randomization for participant not exposed).

Unscheduled visits

Unscheduled visit measurements of laboratory data, vital signs, ECG and ADA will be used for computation of baseline, the last on-treatment value, analysis according to PCSAs, and the shift summaries for safety. They will also be included in the by-visit summaries if they are re-allocated to scheduled visits.

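### Setting below-LLOQ plasma concentrations to zero in every summary makes an arm-visit geometric mean 0 or undefined as soon as one such value occurs

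*SAP*

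**What the plan says.** SAP 1.2 lists "Plasma pre-dose and post-dose concentrations of SAR441566" as the endpoint for the secondary PK objective. SAP 3.7.1.1 says how it is reported: by intervention group, concentrations are "summarized using arithmetic and geometric means", together with SD, SEM, CV%, minimum, median and maximum. The same paragraph then gives the rule for low values: "All concentration values below the lower limit of quantitation (LLOQ) will be treated as zero in all summary statistics". It makes no exception for the geometric mean, does not say what to print when a zero is present, and does not ask for a count of below-LLOQ values.

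No other section fills the gap. Protocol 8.5 promises only descriptive statistics at selected time points, and SAP Table 11 (Appendix 4) gives only sampling windows.

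For two other data types the SAP uses a positive substitute. In SAP 3.6.3.1, safety laboratory values below the limit "will be replaced by half of the LLOQ". In SAP 3.7.1.3, biomarker computations and plots are done "setting values below LLoQ to LLoQ/2", and the number of such values is reported.

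**The concern.** The list of statistics and the zero rule stand next to each other and cannot both be followed to a meaningful result once a below-LLOQ value appears. A stated rule gives a wrong answer here; this is more than a missing detail. Without a prespecified exception, the programmer must decide after the data are in whether to print zero, drop the value without saying so, or leave the cell blank.

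The trial is dose-ranging with five active regimens, and the geometric mean is a natural figure for comparing concentrations between them. The values most exposed to the rule are pre-dose samples, particularly in the 50 mg QD arm, and samples from participants who had missed doses. At stake is whether that column of the PK table can be read in those cells.

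**Working it through.** The documents state no figure on this point, so there is none to reproduce.

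**Inputs**
- Statistic and substitution rule: SAP 3.7.1.1.
- Planned numbers: SAP 1.1. The naive stratum (NTIP) has 24 per arm. The experienced stratum (ETIP) adds 18 in 200 mg BID, 200 mg QD and 100 mg QD only. SAP 3.7.1.1 summarizes by intervention group and does not mention a split by stratum. If the strata are pooled, those three arms have 24 + 18 = 42, and 50 mg QD and 100 mg BID have 24.
- Half-life of about 20 to 30 hours: protocol 4.3.
- LLOQ and below-LLOQ rate: not given, so assumed below.

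**Step 1: effect of one zero.** In product form, GM = (x₁ × … × xₙ)^(1/n). One factor of 0 gives GM = 0. In log form, GM = exp(mean of log x), and log 0 is undefined. This holds for any n and any other values.

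**Step 2: how often it would be triggered.** P(at least one below-LLOQ value) = 1 − (1 − q)ⁿ, with assumed independent rate q per sample:

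| q | n = 24 | n = 42 |
|---|---|---|
| 0.1% | 2.4% | 4.1% |
| 1% | 21% | 34% |
| 2% | 38% | 57% |
| 5% | 71% | 88% |

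Example: 1 − 0.99²⁴ = 0.214. These are planned randomized numbers. With the 10% dropout assumed in SAP Section 4, 24 × 0.9 ≈ 22 gives 20%, 36% and 68% at q = 1%, 2% and 5%, and 42 × 0.9 ≈ 38 gives 32%, 54% and 86%.

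**Step 3: is a high q plausible?** Assume mono-exponential decline, so the fraction remaining after t hours is 2^(−t/half-life). At 24 h (a QD trough) it is 2^(−24/20) = 44% to 2^(−24/30) = 57%. At 48 h (one QD dose missed) it is 19% to 33%. One interval or one missed dose is therefore a modest fall. Whether it crosses the LLOQ depends on the assay limit.

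**Step 4: effect on the other summaries, and of LLOQ/2.** Illustration with simulated lognormal data (assumed median 100, log-SD 0.5), one value replaced:

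| | n = 24 | n = 42 |
|---|---|---|
| GM, all values quantifiable | 106.0 | 91.2 |
| GM, one value set to 0 | 0 | 0 |
| GM, that value omitted | 105.4 | 94.0 |
| GM, LLOQ/2 with LLOQ = 1, 5, 10 | 84.4, 90.2, 92.9 | 83.0, 86.3, 87.7 |
| Arithmetic mean, before and after zero | 111.0, 106.0 | 101.8, 101.2 |

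The arithmetic mean stays usable. With LLOQ/2 the result is GM of the rest × [(LLOQ/2) / GM of the rest]^(1/n). For n = 24 and LLOQ = 1 this is 105.4 × (0.5/105.4)^(1/24) = 84.4.

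**The case against.** The strongest reply is that the trigger should be rare and the harm small.

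On rarity, much of the reply stands. The half-life argues against low troughs in participants who take their doses. Protocol 4.3 reports mean target occupancy of about 95% at trough on 100 mg QD. SAP Section 2 removes an obvious source of unquantifiable samples: "Participants having received only placebo will not be part of the PK population". SAP Table 11 has no Day 1 pre-dose row; its pre-dose windows start with "1 hour before Day 7-21 dose". After the end-of-treatment visit, those who have stopped IMP give no further PK samples. An end-of-treatment sample up to 7 days after the last dose does not obviously fit windows that are tied to a dose.

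Some routes remain. Protocol 7.1.4 allows temporary discontinuation of two or more consecutive doses, and SAP 3.7.1.1 excludes data after a wrong dose but does not mention missed doses. Troughs on 50 mg QD are also summarized. Neither route can be sized without the LLOQ.

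On harm, the reply also largely stands. The summary is descriptive, the failure shows itself as a zero or blank beside a positive median, and PK parameters come from a separate population PK report.

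It is also fair to say that LLOQ/2 for laboratory and biomarker data does not oblige the SAP to use it for PK. Different rules for different data types are not in themselves an inconsistency. The fault is that this rule does not work with this statistic, and rarity does not remove it.

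**Conclusion.** The point holds as a limited one. As written, one below-LLOQ value makes that arm-visit geometric mean 0 or undefined, and nothing elsewhere in the documents repairs it. That part is algebra and needs no assumption.

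How often it would happen is not known. The percentages rest on assumed, independent rates of 1% to 5% per sample and on planned numbers, and the documents' own PK information points towards uncommon rather than frequent.

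A reader might infer three stronger things that the documents do not support:
- **That losing the geometric mean is likely, with up to 88% as the headline, especially in the lowest dose arm.** The 5% rate has no source. The n = 42 figures belong only to 200 mg BID, 200 mg QD and 100 mg QD with strata pooled. The 50 mg QD arm has no ETIP participants, so its figures are those for n = 24.
- **That the secondary PK endpoint is lost.** The arithmetic mean, median, other summaries and individual listings remain available.
- **That exposure-response or efficacy conclusions are affected.** Protocol 8.5 assigns PK parameters and any exposure-response work to population PK and PK/PD analyses reported separately. The efficacy analyses do not use these summaries.

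The correction is worth making because it is cheap and settles the rule before anyone sees which cells are affected.

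**What to change.** Revise the sentence in SAP 3.7.1.1 before database lock:
- keep zero for below-LLOQ values in the arithmetic summaries;
- exempt the geometric mean from the zero rule and use LLOQ/2 there, as in SAP 3.6.3.1 and 3.7.1.3;
- report the number of below-LLOQ values for each arm and visit.

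The cost is one sentence and one extra row in the table. The small downside is that the geometric mean then depends somewhat on the LLOQ. In the illustration, one substituted value at n = 24 puts it 12% to 20% below the geometric mean of the other 23 (92.9 to 84.4 against 105.4), and the count lets the reader see where this applies. Omitting such values and giving the count, or not reporting the geometric mean when any value is below LLOQ, would also be workable. LLOQ/2 has the advantage of being the SAP's own convention, and whichever rule is chosen should be written down in advance.
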